8.1.1 UNANTICIPATED PROBLEM REPORTING

The principal investigator (PI) will report unanticipated problems (UPs) to the reviewing Institutional Review Board (IRB). The UP report will include the following information:

- Protocol identifying information: protocol title and number, PI's name, and the IRB project number;
- A detailed description of the event, incident, experience, or outcome;
- An explanation of the basis for determining that the event, incident, experience, or outcome represents an UP;
- A description of any changes to the protocol or other corrective actions that have been taken or are proposed in response to the UP.

To satisfy the requirement for prompt reporting, UPs will be reported using the following timeline:

- UPs that are serious adverse events (SAEs) will be reported to the IRB within 10 days of the investigator becoming aware of the event, to allow the investigator to conduct an investigation.
- Any other UP will be reported to the IRB and to the DCC/study sponsor within 10 days of the investigator becoming aware of the problem.
- All UPs should be reported to appropriate institutional officials (as required by an institution's written reporting procedures), the supporting agency head (or designee), and the Office for Human Research Protections (OHRP) within 10 days of the IRB's receipt of the report of the problem from the investigator.

8.2 SAFETY AND OTHER ASSESSMENTS

The level and frequency of monitoring are designed to be commensurate with the risks, nature, and complexity of this clinical trial. Additionally, the data safeguarding procedures will adhere to all current standards established under the Common Rule, the Health Insurance Portability and Accountability Act (HIPAA), policies by AHRQ and NIH, and policies established by the Cedars-Sinai Institutional Review Board. All investigators have undergone required trainings in human subjects' protections and have extensive experience in handling sensitivity information. As PI, [name] has ultimate responsibility for monitoring data and safety.

Monitoring procedures will serve the following functions: (1) reviewing the research protocol and plans for data and safety monitoring issues; (2) monitoring data quality, timeliness, survey response rates, and factors that may affect the risks and benefits of the study such as emerging literature; (3) monitoring for potential and actual adverse events, and (4) making recommendations regarding continuation of the trial.

Internal Monitoring Procedures: The study team will learn of potential issues with data and safety for nurses and patients through the following procedures.

Nurses: [name] will meet periodically with nursing unit managers to qualitatively monitor nurses' perceptions of the study, including whether they have any concerns or any potential or actual adverse events have occurred. As Chief Patient Safety Officer, [name] will monitor for increases in the number of referrals of nurses to the Human Resources Department on the intervention nursing units during the study period. Additionally, the Analytical Team will monitor responses to a relevant domain on the AHRQ Hospital Survey on Patient Safety Culture, Nonpunitive Response to Error, which reflects whether nurses feel that they have been blamed for reported incidents. This survey will be deployed before and after the implementation of the SAFE Loop, enabling the research team to detect problems with the first implementation phase before the subsequent phase begins.

Patients: [name] will work with the Cedars-Sinai Patient Safety Department, which handles incident reports, to qualitatively monitor whether there may be any reports addressing risks to patients associated with changes in practice on study nursing units that were implemented in response to the intervention.

Inadvertent Disclosures of Identifiable Information: The team will self-monitor whether data are collected, stored, transmitted, and analyzed in accordance with the Data and Safety Monitoring Plan and for any inadvertent disclosures of sensitive information.

The research team will include data and safety monitoring on the agenda of each routine team meeting, enabling any concerns to be identified and addressed quickly. The study will submit annual progress reports to the Cedars-Sinai Institutional Review Board and meet annually with the external DSM during Years 1 to 4.

External Monitoring Procedures: The DSM will monitor throughout the portions of the study that involve human subjects, including implementation of the SAFE Loop, surveys of nurses, and extraction of data from incident reports and medical records. The DSM will meet with the Executive Oversight Team four times via teleconference to review the Data and Safety Monitoring Plan, proposed study procedures, data safeguarding practices, and data on potential and actual adverse events.

- *Year 1:* The DSM will meet to review study protocols and the Data and Safety Monitoring Plan prior to the start of data collection.
- *Year 2:* The DSM will meet to monitor progress in the study and consider any new information related to risks to nurse and patients. This meeting will represent a project milestone (see timeline) because it will provide a more complete picture of the risks associated with the study.
- *Year 3:* The DSM will meet to monitor progress and any potential or actual adverse events. Additionally, the study Analytical Team will send the external monitoring body the survey responses on Nonpunitive Responses to Error after each deployment of the survey.
- *Year 4:* The DSM will meet after the intervention and data collection are complete to review information on potential or actual adverse events. This meeting will represent a project milestone (see timeline) because it will be the concluding meeting of the DSM.
- *Additional Reviews:* The DSM will reserve the right to request additional interim reviews, in the unlikely event that concerns are raised about data safeguarding or safety.

Investigation of Suspected Adverse Events: Any potential or actual adverse events will be immediately reported to [name] (PI) and [name] (internal DSM). [name] will contact the parties involved to investigate: (1) nature of the event, (2) the type and severity of harm, (3) potential attribution to the research study, (4) circumstances that led up to the event including whether any study procedures deviated from the study protocol, and (5) potential for recurrence. [name] will report this information to the research team, which will discuss how to address the event and to reduce the risk of recurrence.

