2.3 RISK/BENEFIT ASSESSMENT

2.3.1 KNOWN POTENTIAL RISKS

There are two categories of study subjects who will be affected by SAFE Loop:

1. **Nurses** and nursing unit managers who work in the nursing units, and
2. **Patients** who receive care there.

Table of Study Procedures and Associated Risks for Each Group.

Study Procedure	Risks for Nurses	Risks for Patients
1. Organizational Quality Improvement Intervention: Implementation of SAFE Loop in nursing units	Psychological distress or loss of professional reputation may occur if a nurse is blamed for a medication error after an incident report is submitted. Risks are similar to those in usual nursing practice because nurses already submit incident reports.	Medication error. Risks are unlikely but may occur if the nursing units inadvertently implement changes that worsen rather than improve medication safety, as intended.

	To further mitigate the risks, we will train nurses to emphasize reporting of near misses and no-harm events (which are less likely to result in punitive responses by unit managers) and train unit managers in the “just culture” approach, which emphasizes changing systems of care rather than blaming individual nurses when medication errors occur.	
2a. Research data collection: nursing work schedules, to assess nurse eligibility for survey	Inadvertent disclosure of individually identifiable information on nursing work schedules. This data source does not include sensitive information.	Not applicable.
2b. Research data collection: surveys of nurses on attitudes toward reporting and patient safety culture	Inadvertent disclosure of individually identifiable information on nursing survey. Survey does not involve sensitive information and it is already routinely deployed in this hospital.	Not applicable.
3. Research data collection: analysis of incident reports to assess rate and quality of reports	Inadvertent disclosure of individually identifiable information. This data source includes sensitive information such as errors that nurses may have committed. Data to be extracted will not include individually identifiable information about nurses.	Inadvertent disclosure of protected health information (PHI). Incident reports contain patient identifiers and PHI. Data to be extracted will not contain patient identifiers aside from randomly assigned study identification numbers to facilitate linkage to other datasets.

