8.3 ADVERSE EVENTS AND SERIOUS ADVERSE EVENTS

8.3.1 DEFINITION OF SERIOUS ADVERSE EVENTS (SAE)

Nurses:

- *Loss of professional reputation:* Adverse job consequences for a nurse due to study participation, such as having documentation of providing suboptimal care placed in employment/human resources files, will be considered a serious adverse event.
- *Economic harm:* Adverse job consequences for a nurse due to study participation, such as 1) having work hours reduced, 2) being passed up for a professional opportunity, or 3) being dismissed from Cedars-Sinai, will be considered a serious adverse event.
- *Disclosure of individually identifiable information:* Evidence of significant psychological or other harm to nurses due to disclosure of individually identifiable information outside of the study team will be considered a serious adverse event.
- *Psychological distress:* If a nurse reports psychological distress due to study participation (e.g., via loss of professional reputation or economic harm) that interferes with functioning on a prolonged basis or warrants referral to a mental health professional, this will be an serious adverse event.

Patients:

- **Medication error:** A medication error resulting from the SAFE Loop that required caused a patient temporary or permanent physical harm (a preventable adverse drug event) will be considered a serious adverse event.
- **Disclosure of individually identifiable protected health information:** Evidence of significant psychological or other harm to patients due to disclosure of individually identifiable information outside of the study team will be considered a serious adverse event.

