9.4.4 SAFETY ANALYSES

Nurses:

- The Analytical Team will monitor responses to a relevant domain on the AHRQ Hospital Survey on Patient Safety Culture, Nonpunitive Response to Error, which reflects whether nurses feel that they have been blamed for reported incidents. This survey will be deployed before and after the implementation of the SAFE Loop, enabling the research team to detect problems with the first implementation phase before the subsequent phase begins.
- [name] will meet periodically with nursing unit managers to qualitatively monitor nurses' perceptions of the study, including whether they have any concerns or any potential or actual adverse events have occurred.
- [name] will monitor for qualitative increases in the number of referrals of nurses to the Human Resources Department on the intervention nursing units during the study period.

Patients:

- [name] will work with the Cedars-Sinai Patient Safety Department, which handles incident reports, to qualitatively monitor whether there may be any reports addressing risks to patients associated with changes in practice on study nursing units that were implemented in response to the intervention.

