10 SUPPORTING DOCUMENTATION AND OPERATIONAL CONSIDERATIONS

10.1 REGULATORY, ETHICAL, AND STUDY OVERSIGHT CONSIDERATIONS

10.1.1 INFORMED CONSENT PROCESS

10.1.1.1 CONSENT/ASSENT AND OTHER INFORMATIONAL DOCUMENTS PROVIDED TO PARTICIPANTS

We are requesting a waiver of informed consent for implementation of the SAFE Loop intervention (both nurse and patients) and data collection procedures for Aim 1 (incident reports, both nurses and patients), and Aim 3 (adverse medication events, patients).

For nurses participating in Aim 2 (surveys) we are requesting a waiver of consent documentation. As the survey is via REDCap and is not collecting any identifiable information, requiring a signature would be the only link to a subject's identify. An information sheet will be provided with full consent information. Agreeing to complete and submit the survey will indicate their consent to participate.

For nurses participating in the qualitative interviews of implementation, we will provide consent forms describing in detail the study procedures and risks to the participant. Written documentation of informed consent is required prior to starting intervention/administering study intervention. The following consent materials are submitted with this protocol.

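### The only stated source for individual nurse adverse events is the unit manager, whom the protocol names as a possible source of punitive responses; add a confidential route that bypasses the manager

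*Combined protocol and SAP*

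**What the plan says.** Section 8.2 (Internal Monitoring Procedures) sets out how the study team is to learn of safety problems. For nurses it lists three routes, and 9.4.4 repeats them.

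- **Manager meetings.** A named team member "will meet periodically with nursing unit managers to qualitatively monitor" how nurses see the study and whether concerns or adverse events have arisen. No frequency or format is given.
- **Human Resources referrals.** The Chief Patient Safety Officer "will monitor for increases in the number of referrals of nurses to the Human Resources Department on the intervention nursing units". In 9.4.4 this is softened: the officer "will monitor for qualitative increases in the number of referrals of nurses to the Human Resources Department".
- **One survey domain.** Nonpunitive Response to Error, "which reflects whether nurses feel that they have been blamed for reported incidents", is answered by nurses before and after implementation. The Analytical Team "will send the external monitoring body the survey responses on Nonpunitive Responses to Error after each deployment of the survey".

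Section 2.3.1 gives blame after an incident report as the main nurse risk. As mitigation, nurses are trained to favour near misses and no-harm events, "which are less likely to result in punitive responses by unit managers", and managers are trained in just culture. Section 8.3.1 defines serious nurse events as adverse file documentation, job consequences such as "1) having work hours reduced, 2) being passed up for a professional opportunity" or dismissal, harm from disclosure of identifiable information, and prolonged or referral-level distress. Section 10.1.1.1 adds: "We are requesting a waiver of informed consent for implementation of the SAFE Loop intervention".

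**The concern.** The one person asked about individual nurse events is the nurse's own manager. The protocol itself treats that manager as a possible source of the punitive reaction, and also makes the manager the local leader of implementation (6.4). An informant in that position may not know of an event, or may not see it as one.

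The distress definition in 8.3.1 presupposes that a nurse reports the distress, but the text does not say to whom or how. Because consent for the intervention is waived and the survey is deliberately not linked to the SAFE Loop (4.1, 8.1), some nurses may not know that there is a study to which a consequence could be attributed.

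What is at stake is participant safety. The single external monitor, appointed instead of a board, reviews evidence of adverse events to advise on continuing, altering or ending the trial (10.1.6). Section 7.1 intends stopping rules based on severe adverse events. Both depend on events being found. No efficacy estimate is affected.

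**Working it through.** The plan states no detection figure to reproduce, so the check compares the sections and adds one calculation on the survey.

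**1. What each route can reveal**

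| Route (8.2, 9.4.4) | Informant | Asks about individual events? | Limits in the text |
|---|---|---|---|
| Manager meetings | Unit manager | Yes | Periodic, qualitative; informant has a conflict of interest |
| HR referrals | Not stated who refers | No, a count | Intervention units only; no threshold or control comparison |
| Nonpunitive Response to Error | Nurses | No, a score | Two time points per unit |

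The documents do not say which of the consequences in 8.3.1 would generate a referral. That formal file notes and dismissal would reach HR, while reduced hours, a missed opportunity or distress might not, is my assumption. Nor do they say who would impose a job consequence.

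**2. Can the survey show a single event?** Inputs from 9.2 (Aim 2): 1,980 nurses, 85% eligible, 60% response, 20 units.

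- Responses per unit: 1,980 × 0.85 × 0.60 / 20 = 50.49, which reproduces the stated 50.5. For the ten SAFE Loop units: 504.9.
- Largest effect of one respondent moving from 100% to 0% positive: 100 / 50.49 = 1.98 percentage points (pp) on the unit score and 100 / 504.9 = 0.20 pp on the arm score.
- Five harmed nurses at 0.85 × 0.60 = 51% coverage: 5 × 0.51 = 2.55 respondents, so at most 2.55 × 100 / 504.9 = 0.51 pp on the arm score.
- The detectable differences in 9.2 are 7 to 13 pp. They were derived for the two Aim 2 composites. Applied to this domain as an assumption, with no change in controls, they correspond to 0.07 × 504.9 = 35 up to 0.13 × 504.9 = 66 respondents moving fully from positive to negative.

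The domain can therefore register a change in climate but not an event. Survey eligibility is more than half time on one study unit over a six-month period (5.1), so a nurse who was dismissed or moved may also have left the follow-up frame. Section 10.1.1.1 says that the survey collects nothing identifiable, while 10.1.9.1 describes surveys as individually identifiable. These need reconciling, but neither describes tracing a response to an event.

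**3. Other contact with nurses**

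- *Interviews (8.1):* 22 frontline nurses are interviewed after implementation. The listed topics cover fidelity, adaptations, dose, reach, barriers, mechanisms, control-arm exposure and context, but not adverse consequences. Sampling is purposive. If it were a random draw from the roughly 800 eligible nurses in 5.1 (an assumption), the chance of including one particular harmed nurse would be 22 / 800 = 2.75%. The chance of including at least one of five would be about 13% (one minus the product of (778 − i)/(800 − i) for i = 0 to 4).
- *Huddles (6.1.1):* team members meet frontline nurses weekly, but the stated purpose is to prompt and teach reporting. A huddle is not a confidential setting.

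**4. What happens once an event is known.** Section 8.2 sends it to the principal investigator and the internal monitor, and the parties involved are contacted. This step is sound. The gap lies before it, in how an event comes to notice without the manager.

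**The case against.** The strongest reply is that this is a low-risk quality-improvement study with monitoring scaled to that risk, and that two of its three nurse routes do not rely on asking managers. One of them is answered by nurses and goes to the external monitor. Study staff are on the units often, and the interviews are open-ended. Much of this stands, and it rules out several stronger readings.

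- *That the protocol expects managers to punish nurses.* Section 2.3.1 says only that harm may occur, likens the risk to usual practice, and adds just-culture training.
- *That the adverse-event count will be biased toward zero.* No figure in the documents shows this. The text supports a risk of under-detection and no more.
- *That continuing into the second phase rests on that count.* Section 8.2 ties detection of first-phase problems before the next phase to the survey, and 7.1 lets the monitor act on information other than adverse events.
- *That no direct route exists anywhere.* The information sheet, the consent forms, the Data and Safety Monitoring Plan and the first part of 10.1.5 were not available here, and any of them may name a safety contact.

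What the reply does not answer is that, in the sections that set out detection, the manager is the only stated source for individual events.

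**Conclusion.** The point holds as a cheap improvement. In 8.2 and 9.4.4, individual nurse adverse events have one stated source, and that source has a conflict of interest on the protocol's own description. Referral counts and an aggregate score complement it but do not replace it: one respondent moves a unit score by at most 1.98 pp. Events listed in 8.3.1 are therefore at risk of under-detection in the evidence given to the external monitor. The survey domain partly covers the check before the second phase.

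The size of any under-detection cannot be estimated from the documents. The conclusion rests on the response assumptions in 9.2, on the labelled assumption about which consequences reach HR, and on the absence of a direct route from the text available. If such a route exists, what remains is to name it and to make sure that it reaches nurses covered by the consent waiver.

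**What to change.** In 8.2 and 9.4.4:

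1. Keep the manager meetings as one source.
2. Add a direct, confidential contact to the internal Data and Safety Monitor, with the external monitor as alternative, for any adverse consequence of filing an incident report. It should not pass through the unit manager. The internal monitor already receives suspected events under 8.2, so the later steps need no change.
3. Offer it to nurses on all 20 units through the planned fliers and huddle visits. On control units, those planned for the survey (5.5) can carry it. Word it neutrally, about incident reporting in general, so that it does not reveal the SAFE Loop there.
4. If a route already exists in the consent or information materials, the monitoring plan or 10.1.5, name it in 8.2 and extend it to nurses covered by the waiver.

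A question on adverse consequences of reporting could be added to the frontline interviews. It is an optional supplement only, because the interviews are few and take place after implementation.

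The cost is protocol wording and an IRB-approved line on existing fliers, with no new staff. The downside is that some unrelated workplace grievances will arrive and need triage by the internal monitor.

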8.3 ADVERSE EVENTS AND SERIOUS ADVERSE EVENTS

8.3.1 DEFINITION OF SERIOUS ADVERSE EVENTS (SAE)

Nurses:

- *Loss of professional reputation:* Adverse job consequences for a nurse due to study participation, such as having documentation of providing suboptimal care placed in employment/human resources files, will be considered a serious adverse event.
- *Economic harm:* Adverse job consequences for a nurse due to study participation, such as 1) having work hours reduced, 2) being passed up for a professional opportunity, or 3) being dismissed from Cedars-Sinai, will be considered a serious adverse event.
- *Disclosure of individually identifiable information:* Evidence of significant psychological or other harm to nurses due to disclosure of individually identifiable information outside of the study team will be considered a serious adverse event.
- *Psychological distress:* If a nurse reports psychological distress due to study participation (e.g., via loss of professional reputation or economic harm) that interferes with functioning on a prolonged basis or warrants referral to a mental health professional, this will be an serious adverse event.

Patients:

- **Medication error:** A medication error resulting from the SAFE Loop that required caused a patient temporary or permanent physical harm (a preventable adverse drug event) will be considered a serious adverse event.
- **Disclosure of individually identifiable protected health information:** Evidence of significant psychological or other harm to patients due to disclosure of individually identifiable information outside of the study team will be considered a serious adverse event.

